6.2.3 Follow-up period and trial completion

For AE assessment, laboratory tests, recording of ECG and vital signs, and physical examination during the follow-up period, see Sections [5.2.2](#) to [5.2.5](#).

Subjects who discontinue treatment before the end of the planned treatment period should undergo the EoTrial Visit.

All abnormal values (including laboratory parameters) that are assessed as clinically relevant by the investigator will be monitored using the appropriate tests until a return to a medically acceptable level is achieved. (S)AEs persisting after a subject's EoTrial Visit must be followed until they have resolved, have been sufficiently characterised, or no further information can be obtained.

7. STATISTICAL METHODS AND DETERMINATION OF SAMPLE SIZE

7.1 STATISTICAL DESIGN – MODEL

The main objective of this trial is to investigate the pharmacokinetics of digoxin, furosemide, metformin and rosuvastatin given as a cocktail alone (Reference, R) and as a cocktail together with BI 730357 (Test, T) following oral administration on the basis of the primary and secondary pharmacokinetic endpoints, as listed in Sections [2.1.2](#) and [2.1.3](#). The trial is designed to allow intra-subject comparisons and will be evaluated statistically by use of a linear model for logarithmically transformed PK endpoints.

7.2 NULL AND ALTERNATIVE HYPOTHESES

The relative bioavailability of digoxin, rosuvastatin, metformin and furosemide (the cocktail) given alone compared with a combined administration with BI 730357 will be estimated by the ratios of the geometric means (test/reference) for the primary and secondary PK endpoints and their corresponding 2-sided 90% confidence intervals (CIs) will be provided. This method corresponds to the two one-sided t-test procedure, each at the 5% significance level. Since the main focus is on estimation and not testing, a formal hypothesis test and associated acceptance range is not specified.

7.3 PLANNED ANALYSES

Analysis sets

Statistical analyses will be based on the following analysis sets:

- Treated set (TS): The treated set includes all subjects who signed informed consent and were treated with at least one dose of study drug. The treated set will be used for safety analyses.
- Pharmacokinetic parameter analysis set (PKS): This set includes all subjects in the treated set (TS) who provide at least one PK endpoint that was defined as primary or secondary and was not excluded due to a protocol deviation relevant to the evaluation of PK or due to PK non-evaluability (as specified in the following subsection ‘Pharmacokinetics’). Thus, a subject will be included in the PKS, even if he/she contributes only one PK parameter value for one period to the statistical assessment. Descriptive and model based analyses of PK parameters will be based on the PKS.

Adherence to the protocol will be assessed by the trial team. Important protocol deviations (iPD) categories will be suggested in the TSAP; iPDs will be identified no later than in the Report Planning Meeting, and iPD categories will be updated as needed.

Pharmacokinetics

The pharmacokinetic parameters listed in Sections 2.1 [REDACTED] will be calculated according to the relevant SOP of the Sponsor ([001-MCS-36-472](#)).

Plasma and urine concentration data and parameters of a subject will be included in the statistical pharmacokinetic (PK) analyses if they are not flagged for exclusion due to a protocol deviation relevant to the evaluation of PK (to be decided no later than in the Report Planning Meeting) or due to PK non-evaluability (as revealed during data analysis, based on the criteria specified below). Exclusion of a subject's data will be documented in the CTR.

Relevant protocol deviations may be

- Incorrect dose of trial medication taken
- Use of restricted medications

Plasma and urine concentrations and/or parameters of a subject will be considered as non-evaluable, if for example

- The subject experienced emesis that occurred at or before two times median t_{max} of the respective treatment (Median t_{max} is to be determined excluding the subjects experiencing emesis),
- A predose concentration is $>5\%$ C_{max} value of that subject
- Missing samples/concentration data at important phases of PK disposition curve

Plasma/urine concentration data and parameters of a subject which is flagged for exclusion will be reported with its individual values but will not be included in the statistical analyses. Descriptive and inferential statistics of PK parameters will be based on the PKS.

Only concentration values within the validated concentration range and actual sampling times will be used for the calculation of pharmacokinetic parameters. Concentrations used in the pharmacokinetic calculations will be in the same format provided in the bioanalytical report, (that is, to the same number of decimal places provided in the bioanalytical report).

7.3.1 Primary endpoint analyses

Primary analyses

The primary endpoints are specified in Section 2.1.2. The analysis will be based on the PKS and will be descriptive in nature.

The statistical model used for the analysis of the primary endpoints $AUC_{0-\infty}$ and C_{max} of each of the variables rosvastatin, digoxin, metformin and furosemide will be an analysis of variance (ANOVA) model on the logarithmic scale. That is, the PK endpoints will be log-transformed (natural logarithm) prior to fitting the ANOVA model. This model will include effects accounting for the following sources of variation: 'subjects' and 'treatment'. The effect 'subject' will be considered as random, whereas the effect 'treatment' will be considered as fixed. The model is described by the following equation:

$$y_{km} = \mu + \pi_k + s_m + e_{km}, \text{ where}$$

y_{km} = logarithm of response measured on subject m receiving treatment k,

μ = the overall mean,

π_k = the k^{th} treatment effect, $k = 1, 2,$

s_m = the effect associated with the m^{th} subject, $m = 1, 2, \dots, 15$

e_{km} = the random error associated with the m^{th} subject who received treatment k.

where $s_m \sim N(0, \sigma_B^2)$ i.i.d., $e_{km} \sim N(0, \sigma_W^2)$ i.i.d. and s_m, e_{km} are independent random variables.

Point estimates for the ratios of the geometric means (test/reference) for the primary endpoints (see Section 2.1) and their two-sided 90% confidence intervals (CIs) will be provided.

For each endpoint, the difference between the expected means for $\log(T)$ - $\log(R)$ will be estimated by the difference in the corresponding adjusted means (Least Squares Means). Additionally their two-sided 90% confidence intervals will be calculated based on the residual error from the ANOVA and quantiles from the t-distribution. These quantities will then be back-transformed to the original scale to provide the point estimate and 90% CIs for each endpoint.

In addition to the model based approach all parameters will be calculated and analysed descriptively.

7.3.2 Secondary endpoint analyses

The secondary endpoint (refer to Section 2.1.3) will be calculated according to the BI SOP 'Standards and processes for analyses performed within Clinical Pharmacokinetics/ Pharmacodynamics' (001-MCS-36-472) and will be assessed statistically using the same methods as described for the primary endpoints.

7.3.4 Safety analyses

Safety will be analysed based on the assessments described in Section [2.2.2.2](#). All treated subjects (TS, refer to Section [7.2](#)) will be included in the safety analysis. Safety analyses will be descriptive in nature and based on BI standards. No hypothesis testing is planned.

For all analyses, the treatment actually administered (= treatment at onset of AE) to the subject will be used (any deviations from the planned treatment will be discussed in the minutes of the Report Planning Meeting).

Treatments will be compared in a descriptive way. Tabulations of frequencies/proportions will be used to evaluate categorical (qualitative) data, and tabulations of descriptive statistics will be used to analyse continuous (quantitative) data.

Measurements (such as ECG, vital signs, or laboratory parameters) or AEs will be assigned to treatments (see Section [4.1](#)) based on the actual treatment at the planned time of the measurement or on the recorded time of AE onset (concept of treatment emergent AEs). Therefore, measurements planned or AEs recorded prior to first intake of trial medication will be assigned to the screening period, those between trial medication intake and end of REP (see Section [1.2.3](#)) will be assigned to the treatment period. Events occurring after the REP but prior to next intake or end of trial termination date will be assigned to 'follow-up'. In case of two or more treatments, the follow-up will be summarized according to the previous treatment. These assignments including the corresponding time intervals will be defined in detail in the TSAP. Note that AEs occurring after the last per protocol contact but entered before final database lock will be reported to Pharmacovigilance only and will not be captured in the trial database.

Additionally, further treatment intervals (analysing treatments) may be defined in the TSAP in order to provide summary statistics for time intervals, such as combined treatments, on-treatment totals, or periods without treatment effects (such as screening and follow-up intervals).

Adverse events will be coded using the Medical Dictionary for Regulatory Activities (MedDRA). Frequency, severity, and causal relationship of AEs will be tabulated by treatment, system organ class, and preferred term. SAEs, AESIs (see Section [5.2.5.1](#)), and other significant AEs (according to ICH E3) will be listed separately.

Previous and concomitant therapies will be presented per treatment group without consideration of time intervals and treatment periods.

Laboratory data will be compared to their reference ranges. Values outside the reference range as well as values defined as possibly clinically significant will be highlighted in the listings. Additionally, differences from baseline will be evaluated.

Vital signs or other safety-relevant data will be assessed with regard to possible on-treatment changes from baseline.

Relevant ECG findings will be reported as AEs.

7.4 INTERIM ANALYSES

No interim analysis is planned.

7.5 HANDLING OF MISSING DATA

7.5.1 Safety

It is not planned to impute missing values for safety parameters.

7.5.2 Pharmacokinetics

Handling of missing PK data will be performed according to the relevant Corporate Procedure ([001-MCS-36-472](#)).

[figure not shown]
PK parameters that cannot be reasonably calculated based on the available drug concentration-time data will not be imputed.

7.6 RANDOMISATION

This is a non-randomised trial.

7.7 DETERMINATION OF SAMPLE SIZE

It is planned to enter a total of 15 subjects in the trial, because this sample size is considered sufficient to achieve the aims of this exploratory trial. With this sample size, the following precision in estimating the ratio of geometric means (test/reference) can be expected with 95% probability. Precision is defined as the ratio of upper CI limit to the relative BA estimate. Note that the precision is independent of the actual ratio of geometric means.

For various assumptions around the gCV of 30% , Table [7.7: 1](#) provides an overview of the achievable precision for estimating the ratio of geometric means (test/reference). For illustrative purposes, the expected 90% confidence intervals are displayed for different values of the ratios T/R of geometric means.

Table 7.7: 1 Precision that can be expected with 95% probability and illustrative two-sided 90% confidence intervals around the ratios of geometric means (T/R) for different gCVs in a 2-period fixed-sequence trial ($N=15$)

gCV [%]	Precision upper CL / relative BA estimate	Ratio [%]*	Lower CL [%]	Upper CL [%]
20.0	1.18	100	84.73	118.02
20.0	1.18	150	127.10	177.03
20.0	1.18	200	169.47	236.04
25.0	1.23	100	81.39	122.87
25.0	1.23	150	122.08	184.31
25.0	1.23	200	162.77	245.74
30.0	1.28	100	78.23	127.83
30.0	1.28	150	117.34	191.75
30.0	1.28	200	156.45	255.67
35.0	1.33	100	75.25	132.89
35.0	1.33	150	112.87	199.34
35.0	1.33	200	150.50	265.78

*Ratio of geometric means (test/reference) for a PK endpoint is defined by $\exp(\mu_T)/\exp(\mu_R)$.

The expected 90% confidence interval limits in the table were derived by

$$CI \text{ limit}_{\text{upper,lower}} = \exp(\ln(\theta) \pm \omega),$$

with θ being the ratio (T/R) on original scale and ω the distance from the estimate θ to either confidence interval limit on the log-scale, which was obtained from the achievable precision on the original scale.

The calculation was performed as described by Julious [R11-5230] using R Version 3.6.1.

8. INFORMED CONSENT, TRIAL RECORDS, DATA PROTECTION, PUBLICATION POLICY, AND ADMINISTRATIVE STRUCTURE

The trial will be carried out in compliance with the protocol, the ethical principles laid down in the Declaration of Helsinki, in accordance with the ICH Harmonized Guideline for Good Clinical Practice (GCP), relevant BI Standard Operating Procedures (SOPs), the EU regulation 536/2014, and other relevant regulations. Investigators and site staff must adhere to these principles.

Standard medical care (prophylactic, diagnostic, and therapeutic procedures) remains the responsibility of the subject's treating physician.

The investigator will inform the sponsor immediately of any urgent safety measures taken to protect the trial subjects against any immediate hazard, as well as of any serious breaches of the protocol or of ICH GCP.

The Boehringer Ingelheim transparency and publication policy can be found on the following web page: trials.boehringer-ingelheim.com. As a general rule, no trial results should be published prior to archiving of the CTR.

The terms and conditions of the insurance coverage are made available to the investigator and the subjects, and are stored in the ISF.

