3.3.5 Replacement of subjects

In case more than 3 subjects do not complete the trial, the Clinical Trial Leader together with the Trial Pharmacokineticist and the Trial Statistician are to decide, if and how many subjects will be replaced. A replacement subject will be assigned a unique trial subject number.

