6.2 IMPORTANT PROTOCOL DEVIATIONS

Table 6.2: 1 Handling of important protocol deviations (iPDs)

iPD code	iPD Category & Brief Description	Excluded from which analysis set
A1	Inclusion Criteria Not Met	None
A2	Exclusion Criteria violated	None
B1	Informed consent not available/not done	TS, PKS [REDACTED]
B2	Informed consent too late	None
C1	Incorrect trial medication intake	PKS [REDACTED]
C3	Non-compliance	PKS [REDACTED]
C4	Medication code broken inappropriately	None
C5	Incorrect intake of trial medication	PKS [REDACTED]
C6	Improper washout between treatments	PKS [REDACTED]
D1	Prohibited medication use	PKS [REDACTED]
D2	Mandatory medication not taken	PKS [REDACTED]
D3	Improper washout of concomitant medication	PKS [REDACTED]
E1	Certain violations of procedures used to measure primary or secondary data	PKS [REDACTED]
F1	Certain violations of time schedule used to measure primary or secondary data	PKS [REDACTED]
G1	Incorrect intake of meal	PKS [REDACTED]

Table 6.2: 2 Handling of non-important COVID-19 related protocol deviations

PD code	PD Category	Excluded from which analysis set
Q1	Missed examination	None
Q2	(Partially) missed visit	None
Q3	Drug shipment	None

Consistency check listings (for identification of deviations from time windows) and a list of protocol deviations (e.g. deviations in drug administration, in blood sampling times, etc.) will be provided to be discussed at the Report planning meeting (RPM). At this meeting, it will be decided whether a discrepant data value can be used in analyses or whether it must be corrected in the clinical database. Each protocol deviation must be assessed to determine whether it is an iPD and whether it is COVID-19 related. For definition of iPDs, and for the process of identification of these, refer to the BI reference document "Identify and Manage Important Protocol Deviations (iPD)" ([1](#)).

If any iPDs are identified, they are to be summarised into categories and will be captured in the RPM minutes. Categories which are considered to be iPDs in this trial are defined in the integrated quality and risk management plan (IQRMP). If the data show other iPDs, the definition in the IQRMP will be supplemented accordingly by the time of the RPM.

iPDs will be summarised and listed. Additionally, protocol deviations associated with COVID-19 disruption (non-important and important protocol deviations) will be summarised and listed.

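### Does the 95% precision statement for 15 entered subjects need correcting because Table 7.7:1 assumes 15 complete Test/Reference pairs?

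*Protocol*

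**What the plan says.** Protocol Section 7.7 justifies the sample size by precision, not power: "It is planned to enter a total of 15 subjects in the trial, because this sample size is considered sufficient to achieve the aims" of what it calls an exploratory trial. It continues: "With this sample size, the following precision in estimating the ratio of geometric means (test/reference) can be expected with 95% probability". It then defines the measure: "Precision is defined as the ratio of upper CI limit to the relative BA estimate". Table 7.7:1, headed N=15, gives 1.18, 1.23, 1.28 and 1.33 for gCVs of 20, 25, 30 and 35%. Section 7.7 describes the precision as achievable and the intervals as illustrative.

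Other sections determine how many subjects contribute a pair:

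- Section 3.3.5 leaves replacement to a joint decision by the trial team, triggered as follows: "In case more than 3 subjects do not complete the trial".
- Section 7.3 of the protocol defines the PK analysis set (PKS) broadly: "Thus, a subject will be included in the PKS, even if he/she contributes only one PK parameter value for one period".
- Section 7.3.1 fits subject and treatment on the log scale. The subject effect "will be considered as random, whereas the effect" of treatment is fixed.
- Section 7.5.2: "PK parameters that cannot be reasonably calculated based on the available drug concentration-time data will not be imputed".
- SAP Table 6.2:1 lists deviations that remove a subject from the PKS, for example "Certain violations of time schedule used to measure primary or secondary data".

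**The concern.** The 95% probability is attached to a sample size that the text defines as subjects entered, whereas the calculation needs subjects with an evaluable value in both periods. The plan's own rules tolerate a gap between the two. Up to three non-completers trigger no replacement discussion, parameters that cannot be calculated are not imputed, and several deviation categories exclude a subject from the PKS. Period 2 also asks for 13 days of twice-daily dosing, much of it at ambulatory visits, so some loss between periods is plausible.

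The precision statement is the only quantitative support for N=15 that the documents show. If it held only under perfect retention, a reader could expect narrower intervals than the trial is likely to deliver.

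**Working it through.** **Inputs.** From Section 7.7: 15 subjects, 95% assurance, gCV 20 to 35% (taken as within-subject). From Sections 7.2 and 7.3.1: two-sided 90% interval, ANOVA residual error, t-quantiles. With n complete pairs the residual has n − 1 degrees of freedom.

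**Formula.** With σ_w = √ln(1 + gCV²):

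- expected-variance half-width on the log scale: h_n = t(0.95, n−1) · √(2/n) · σ_w
- half-width met with 95% probability: ω_n = h_n · √[χ²(0.95, n−1)/(n−1)]
- precision: exp(ω_n)

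**Reproducing the plan, n = 15, gCV 30%.** σ_w = √ln(1.09) = 0.2936. h₁₅ = 1.7613 × 0.3651 × 0.2936 = 0.1888. ω₁₅ = 0.1888 × √(23.685/14) = 0.2456. exp(0.2456) = 1.278, giving 78.23 to 127.83 around a ratio of 100%, exactly as printed. All 12 rows reproduce to two decimals. Using 13 degrees of freedom gives 1.283, and dropping the assurance factor gives 1.208, so neither alternative reproduces the table.

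**Probability of still reaching the tabulated precision with n pairs.** P_n = F[(n−1)(ω₁₅/h_n)²], where F is the χ² distribution function on n − 1 degrees of freedom. For n = 12, h₁₂ = 1.7959 × 0.4082 × 0.2936 = 0.2152, the argument is 11 × (0.2456/0.2152)² ≈ 14.32 (unrounded inputs), and P₁₂ = 0.784. σ_w cancels, so the result is the same for every gCV.

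| Complete pairs | P(tabulated precision met) | 95%-assured precision, gCV 30% | Interval at ratio 100% |
|---|---|---|---|
| 15 | 95.0% | 1.278 | 78.23–127.83 |
| 14 | 91.2% | 1.294 | 77.28–129.40 |
| 13 | 85.7% | 1.312 | 76.21–131.21 |
| 12 | 78.4% | 1.334 | 74.99–133.36 |

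A simulation with 400,000 replicates per row agrees: 94.9, 91.2, 85.7 and 78.5%.

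**Comparison with the table's own range.** With 12 pairs, the 95%-assured precision is 1.21, 1.27, 1.33 and 1.40 for gCVs of 20, 25, 30 and 35%. The printed 15-pair values one row higher (gCV 25, 30 and 35%) are 1.23, 1.28 and 1.33. So 12 pairs at gCV 20 or 25% stay within the next printed row, and 12 pairs at 30% (1.334) about match the 35% row (1.329 unrounded). Three lost pairs at 30% equal a rise in gCV to about 35.5%: ω₁₂/ω₁₅ = 1.172, σ_w becomes 1.172 × 0.2936 = 0.344, and √(exp(0.344²) − 1) ≈ 0.355. Only 12 pairs at gCV 35% (1.40) lies clearly outside the printed range.

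**How likely is the 12-pair case?** The documents give no loss rate. Assuming independent loss of 3, 5 or 10% per subject, the chance of three or more losses among 15 is about 1, 4 or 18%. Averaged over the number lost, the probability of meeting the tabulated precision is about 93, 92 or 88%.

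**One-period subjects.** Take 12 pairs plus three Reference-only subjects in the random-subject model, with within-subject gCV 30% and an assumed between-subject gCV of 20 to 80% (not in the documents). The probability is about 80 to 83% if the variance ratio is known, and 80 to 88% if it is estimated by REML. The unpaired data help a little but do not restore 95%.

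**The case for a change.** The strongest case for a change is that N is never defined as evaluable pairs, that the sentence before the table defines the sample size as subjects entered, and that a single lost pair already takes the probability below 95%. In a trial about estimation, precision stands in for power, so its condition ought to be written down. Two sentences would do it.

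The arithmetic in that case stands in full, and so does the observation that the assumption is unstated. What does not stand is the step from there to a defect. Section 7.7 makes a planning statement conditional on N=15 and promises nothing about retention. Twelve is also not a firm floor or a forecast. Section 3.3.5 counts subjects who do not complete the trial, which differs from lost pairs in both directions. A subject who leaves after Period 2 sampling but before the final examination still gives a pair, while a completer with a non-calculable endpoint does not. A 12-pair sentence would therefore describe one scenario among several.

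**Conclusion.** No change is needed. Table 7.7:1 is correct for what it computes, and the unstated condition of 15 evaluable pairs per endpoint is one that a statistician reading a paired calculation headed N=15 would supply. If pairs are lost, the 95%-assured precision at gCV 30% widens from 1.28 to 1.29, 1.31 or 1.33 for 14, 13 or 12 pairs, which is largely within the variation the table already displays.

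Nothing downstream rests on the figure: there is no hypothesis test and no acceptance range, and the reported 90% confidence intervals are computed from the data obtained, so they will show whatever precision was achieved. Following the plan as written gives the same estimates and intervals as following an amended one. A note that the table assumes 15 evaluable pairs would be harmless but optional.

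The probabilities by number of pairs follow from the plan's own inputs. The averages over losses and the random-subject figures rest on assumed loss rates and between-subject variability that the documents do not give.
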